11.6 Diary Reported Bleeding and Cramping/Pain Analysis

11.6.1 Months 1-24

For each 28-day cycle and each 84 and 90 day interval post-insertion, the incidence of on-treatment cramping/pain (none, mild, moderate, severe) and bleeding (none, spotting, light flow, medium flow, heavy flow) will be calculated based on diary entries and presented by treatment group. Summaries of the following types will be presented:

- Incidence of cramping/pain by 28-day cycle and 84 and 90 day intervals post-insertion (none vs. ≥ 1 day; 1-3, 4-7, >7 , and >20 days)

- Incidence by of bleeding by 28-day cycle and 84 and 90 day intervals post-insertion (none vs. spotting vs. bleeding; none vs. ≥ 1 day; 1-3, 4-7, >7 , and >20 days; no bleeding vs. any bleeding)
- Incidence of cramping/pain by highest severity or bleeding by greatest intensity by cycle and 84 and 90 day intervals post-insertion. At each level of subject summarization a subject is classified according to the highest severity or intensity if the subject reported one or more events.

Descriptive continuous-based statistics (mean, standard deviation, median, minimum, maximum) will be used to summarize the number of days of reported cramping and bleeding and/or spotting during each 28-day cycle and each 84 and 90-day interval. The number of spotting days and the number of bleeding days (light flow, moderate flow, heavy flow combined and each category separately) will also be summarized using this approach. For cramping/pain, this will also be presented within each severity rating, i.e., the total number of reported days will be broken down into the number of days of mild, moderate, and severe cramping/pain.

11.6.2 After Month 24

The incidence of reported cramping every three months after Month 24 will be reported using the categories which appear in parentheses below:

- Over the last 3 months has the subject had any menstrual cramping/pain? (Yes/No)
- Did the cramping/pain occur mainly when the subject was having any bleeding or spotting? (Yes/No)
- The worst cramping/pain experienced during these months (mild, moderate, severe)

The incidence of bleeding and/or spotting will be presented in a similar fashion based on the following questions and categories of response:

- Over the last 3 months has the subject had any menstrual bleeding/spotting?
- What was the main pattern of bleeding/spotting the subject experienced for these months? (Just Spotting, Irregular Bleeding, Regular Bleeding [periods])
- The heaviest bleeding experienced for these months (Spotting, Light Flow, Normal Flow, Heavy Flow)

11.7 Site Diaries

A Site Diary was originally implemented to characterize subject bleeding and cramping after Month 24. The Site Diary had identical bleeding and cramping questions as the Subject Diary for Months 1-24. The Site Diary was replaced with the Bleeding/Cramping Form. Those subjects for which the Site Diary was completed before the initiation of the Bleeding/Cramping Form will have similar analysis performed as for Months 1-24 for bleeding and cramping pain as outlined in section 11.6.1.

11.8 Insertion

All insertion analyses will be presented separately by inserter type, SHI-001 new inserter and original inserter, and combined data for both inserters.

The number and percentage of subjects with a successful insertion and where rigid cervical dilation or local anesthesia was used will be presented by treatment group. The distribution of easy, neutral, or difficult insertions will be summarized by treatment group. The summaries will be presented by insertion attempt.

Summaries will also be presented by inserter type for other inserter-related outcomes, such as the number and percentage of subjects where insertion failure occurred, difficulty of insertion, use of cervical dilation, perforation, expulsion, and insertion-related bleeding and cramping.

Some subjects will be enrolled (assigned in the IVRS) and will meet the protocol defined IUS insertion failure, which is when, after contact with the cervical os by the inserter, completion of IUS insertion is not achieved. However, some of these insertion failures are unrelated to the study IUS or inserter and such cases will not be analyzed as insertion failures. Examples of such situations include, but are not limited to:

- withdrawal of consent after enrollment and before IUS placement
- cervix could not be visualized
- inserter became contaminated
- subject could not tolerate sounding
- uterus could not be sounded
- uterus sounded to < 5.5 cm
- enrolled but determined not to be eligible before IUS placement

- prior IUD in uterus could not be removed.

Subjects who had a failed first insertion but never came back for a second attempt are considered to be a failed insertion and not a discontinuation due to withdrawal of consent or lost to follow-up.

11.9 Continuation, Expulsion, and Removal Rates

Cumulative rates of IUS continuation, expulsion, and safety-related removal at 6 months, Years 1, 2, 3, 4, 5, 6, 7, 8, 9 and 10 will be summarized. Time to event will be calculated as the date of continuation/expulsion/removal minus the date of IUS insertion plus one. Subjects without a continuation/expulsion/removal will be censored at the last contact date (as described in Section 5.4) and failure time will be calculated as the last contact date minus the date of IUS insertion plus one. Subjects who report an expulsion that is not confirmed by the study site will be censored. The safety-related removal rates may also be summarized by MedDRA preferred term in the same manner.

Expulsion rates including analysis of complete and partial expulsions by inserter type, parity and duration of use (by year) in the Safety Population will also be summarized.

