6.6 Study Treatment Completion/Early Discontinuation

Study treatment completion will occur at the end of 60 months of Mirena IUS use, 96 months of LNG20 IUS use for the 36-45 year old enrollment group or 121 months of LNG20 IUS use in the 16-35 year old enrollment group. The visit should occur within 14 days before or after the completion of 60 months of Mirena use or 96 months for the LNG20 IUS 36-45 year old enrollment group; the visit should occur within 7 days before or after the completion of 121 months of use for the LNG20 IUS 16-35 year old enrollment group. The same assessments should be performed if Early Discontinuation occurs.

- Inquire about last intercourse; if possible, any subjects who had intercourse (with intravaginal ejaculation) within the preceding 24 hours should have the Discontinuation Visit rescheduled to a time more than 24 hours from intercourse.
- Collect diaries and review for appropriate completion. Confirm compliance with study IUS by reviewing contraception method(s) documented in diaries since the last scheduled study contact.
- Complete Bleeding/Cramping Form (**only if discontinuation after Month 24**)
 - Include only information since the last time the form was completed;
 - If the last study visit or contact (phone or email) was more than 3 months ago, only include the information for last 3 months;

- If Early Discontinuation is during Months 25- 27, include only information beginning with Month 25
- Review of adverse events or changes in medical history
- Review of concomitant medications
- Inquire about change in sexual partner
- Collection of blood sample for:
 - Hemoglobin if not done within the last 3 months
 - Plasma levonorgestrel (only if after Month 36 or for subjects participating in the PK Substudy) if not done within the last 3 months
- High sensitivity urine pregnancy test (if positive, see Sections 7.4 and 7.5)
- Weight and blood pressure
- Breast and pelvic exam (if not performed within the last 3 months)
- Any clinically indicated physical examination
- Pap test if indicated, see section 6.11
- STD testing:
 - Chlamydia testing for all subjects 25 years old or younger who have not had any testing within the last 6 months
 - Chlamydia and gonorrhea testing for any subject following a change in sexual partner since the last study visit. In addition HIV and any other appropriate STD testing should be performed as recommended by the CDC

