9.8 Key Secondary Outcomes

The Pearl Index analysis described above for the primary outcome will also be performed for use during years 3, 4, 5, 6, 7, 8, 9 and 10 using the MITT population. The Pearl Index will be calculated for use during years 3, 4, 5, 6, 7, 8, 9 and 10 with a goal of each having acceptable precision (defined as the upper bound of the 95% confidence interval being no more than 1 unit above the point estimate). Other Secondary Outcomes

All secondary outcomes will be analyzed using the Safety Population unless noted otherwise.

- **Pregnancy Rates**

Pearl indices and life table pregnancy analyses will also be prepared for the PP population during years 3, 4, 5, 6, 7, 8, 9 and 10 unless the populations are essentially the same as the MITT population. Kaplan-Meier methods will be used to estimate the cumulative pregnancy percentage for years 1 through 10 for each treatment group using the MITT population.

- **IUS Continuation Rates**

Cumulative IUS continuation rates at 1 year, 2 years, 3 years, 4 years, 5 years, 6 years, 7 years, 8 years, 9 years and 10 years will be summarized for each treatment group, as applicable, using Kaplan-Meier methods.

- **IUS Expulsion Rates**

Cumulative IUS expulsion rates at 1 year, 2 years, 3 years, 4 years, 5 years, 6 years, 7 years, 8 years, 9 years and 10 years will be summarized for each treatment group, as applicable, using Kaplan-Meier methods.

- **IUS Safety-Related Removal Rates**

Cumulative IUS safety-related removal rates at 1 year, 2 years, 3 years, 4 years, 5 years, 6 years, 7 years, 8 years, 9 years and 10 years summarized for each treatment group, as applicable, using Kaplan Meier methods.

- **Vaginal Bleeding Patterns**

Vaginal bleeding patterns (none, spotting, and light, normal, or heavy flow [bleeding]) will be summarized by incidence and duration of bleeding. Baseline vaginal bleeding is recorded on the Menstrual History CRF based on menstrual characteristics when not using hormonal contraception.

Based on WHO terminology, bleeding and spotting are defined as:

- Bleeding: any bloody vaginal discharge for which protection, such as pads is used.
- Spotting: any bloody vaginal discharge for which protection is not used (for women who use mini pads for daily protection, extra protection is not required); if spotting and bleeding occur on the same day, it is recorded as a bleeding day.

- **Dysmenorrhea**

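### SAP 11.9 has no censoring rule for scheduled end-of-treatment removal, so read literally it lowers the Year 8 continuation rate for LNG20 36-45 and, if tabulated, the Year 5 rate for Mirena

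*SAP*

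**What the plan says.** SAP 11.9 covers three rates together: "Cumulative rates of IUS continuation, expulsion, and safety-related removal at 6 months, Years 1, 2, 3, 4, 5, 6, 7, 8, 9 and 10". One timing rule serves all three: "Time to event will be calculated as the date of continuation/expulsion/removal minus the date of IUS insertion plus one". One censoring rule follows: "Subjects without a continuation/expulsion/removal will be censored at the last contact date (as described in Section 5.4"). The only special case in the section is that an expulsion not confirmed by the site is censored. Protocol 9.8 says that continuation "will be summarized for each treatment group, as applicable, using Kaplan-Meier methods".

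Protocol 6.6 fixes when the IUS comes out: "Study treatment completion will occur at the end of 60 months of Mirena IUS use, 96 months of LNG20 IUS use for the" 36-45 group, and 121 months for LNG20 16-35. For the first two groups, "The visit should occur within 14 days before or after the completion of 60 months of Mirena use or 96 months". For the third, "the visit should occur within 7 days before or after the completion of 121 months of use for the LNG20 IUS 16-35" group. Removal is one of the procedures at that visit.

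Continuation at each year is a listed secondary outcome in Protocol 3.2.3. Years 6 to 8 are for LNG20 subjects only, and Years 9 and 10 for the 16-35 group only.

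**The concern.** A continuation rate should describe women who stop before the end of planned use. Every woman who completes treatment also has a removal date, and SAP 11.9 gives no way to tell the two apart. For LNG20 36-45 and for Mirena, the completion window opens 14 days before the last landmark at which the group is reported. Completers seen in those 14 days would become failures. The drop at that landmark would then reflect when visits were booked.

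The LNG20 16-35 group escapes because its removal date lies beyond 10 years. The protocol's summary of changes says Month 121 was added so that use through 10 years would be complete. No such margin exists at Month 60 or Month 96.

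**Working it through.** **The plan's own figure.** The documents state no 5-year or 8-year continuation rate. The nearest figure is the 76% cumulative discontinuation over 10 years in SAP section 4 and Protocol 9.1. It does not follow from the yearly ceilings beside it (20%, 19%, 17%, then 16% in each of years 4 to 10):

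- 0.80 × 0.81 × 0.83 × 0.84^7 = 0.1587, so 84.1% discontinued, not 76%.
- To reach 76%, years 4 to 10 would have to average about 10.9% per year.

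Both baselines are therefore carried below.

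**Retention as the window opens.**

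| | Yearly ceilings | Fitted to 76% |
|---|---|---|
| Year 5 | 0.80 × 0.81 × 0.83 × 0.84^2 = 0.3795 | 0.427 |
| Year 8 | 0.80 × 0.81 × 0.83 × 0.84^5 = 0.2249 | 0.302 |

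**Share of the window before the landmark.** SAP 5.4 converts years at 365.25 days, so Year 5 is day 1,826.25 and Year 8 is day 2,922. Event time is removal minus insertion plus one.

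- Month 60 ± 14 days gives event times 1,813 to 1,841, of which 14 of 29 are on or before 1,826.25.
- Month 96 ± 14 days gives event times 2,909 to 2,937, of which 14 of 29 are on or before 2,922.

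**Effect on Kaplan-Meier.** If S is continuation just before the window and a share f of completers is removed on or before the landmark, counting each as an event gives S × (1 − f). With f = 0 there is no fall; with f = 1 the rate is 0%.

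| | S | f | Rate read |
|---|---|---|---|
| LNG20 36-45, Year 8, ceilings | 22.5% | 14/29 | 0.2249 × 15/29 = 11.6% |
| Mirena, Year 5, ceilings | 38.0% | 14/29 | 0.3795 × 15/29 = 19.6% |
| LNG20 36-45, Year 8, fitted to 76% | 30.2% | 0.5 | 15.1% |
| Mirena, Year 5, fitted to 76% | 42.7% | 0.5 | 21.4% |

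**Simulation check** (400 runs per group, 150 and 159 women, yearly ceilings, uniform window). Counting every removal took LNG20 36-45 from 22.6% just before the window to 11.7% at Year 8, and Mirena from 38.1% to 19.4% at Year 5. Censoring scheduled removals gave 22.4% and 37.7%.

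**LNG20 16-35.** The earliest scheduled removal is about 121 × 30.4375 − 7 = day 3,676, after 10 years (3,652.5 days). No effect.

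**Pooled LNG20 at Year 8.** (1,600 × 0.2249 + 150 × 0.116) / 1,750 = 21.6% against 22.5%, a fall of under 1 point.

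**Expulsion and safety-related removal.** A scheduled removal is neither event, so these rates do not move in this way.

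**The case against.** The strongest reply is that SAP 11.9 never says a scheduled removal is a failure. Its event term is shorthand for three rates at once, and continuation cannot literally be a failure event. Removal there might mean the safety-related removal named a sentence earlier. Elsewhere the documents separate completion from early stopping: Protocol 6.6 in its title, SAP 7.1 on disposition and SAP 11.13.1 on the final visit. An analyst could censor completers without contradicting the plan.

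This stands in part: the point rests on a literal reading and a missing rule, not on an explicit instruction. But reading removal as safety-related only would also drop removals at a woman's own request, which cannot be meant for continuation. And where the SAP wants exceptions it writes them, as for unconfirmed expulsions here and for insertion failures in 11.8.

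A reader might also infer that Mirena will be shown at a disadvantage to LNG20 at 5 years. The documents do not establish this. SAP section 3 limits Mirena data to listed tables that leave out continuation, and the SAP prevails over the protocol. Protocol 3.2.3 and 9.8 and SAP 5.1 point the other way. Mirena is in any case an informative comparator only, with no formal testing.

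The size is also open to challenge. Actual visit timing is unknown, and the discontinuation rates are sample-size ceilings, not forecasts for Mirena users or for women aged 36-45. That is why the figures above are illustrations within a range of no fall to total. A 364-day year would give smaller shares, but in the SAP that year belongs to the cycle-adjusted pregnancy life table; SAP 5.4 uses 365.25 days.

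**Conclusion.** The point holds in limited form. As written, SAP 11.9 turns some on-schedule completers into discontinuations at one landmark per affected group: Year 8 for LNG20 36-45, and Year 5 for Mirena if that rate is tabulated. Under the stated assumptions the rate reads about half its proper value: about 12% against 22% and 20% against 38%, or about 15% against 30% and 21% against 43% on the baseline fitted to 76%.

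These figures assume that the plan's discontinuation rates carry over to both groups. The first pair also assumes uniform visit timing and a 365.25-day year; the second assumes that half the completers are removed by the landmark. It would go too far to say that final-year estimates as a whole measure scheduling, since only the last 14 days before one landmark are involved, or that the pooled LNG20 rate is materially lowered. These are descriptive secondary rates. The correction is still worth making, because two reasonable programmers could produce very different tables.

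**What to change.** In SAP 11.9:

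- Define the continuation event as removal or expulsion before scheduled treatment completion.
- Censor a removal at the Treatment Completion visit (Month 60 Mirena, Month 96 LNG20 36-45, Month 121 LNG20 16-35) on the date of removal.
- State the landmark day for each year, using the 365.25-day year of SAP 5.4.

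There is no need to report the final-year rate at the opening of the completion window as well. Once completers are censored, the landmark estimate is already about right, and an earlier reporting day for two groups would add an inconsistency.

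The cost is a few sentences and one programming condition. Completion and reason for discontinuation are already summarized under SAP 7.1. No visit, window or clinical procedure changes.

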11.10 Fertility Rates Post-Removal

Cumulative fertility rates for each month of the first year following IUS removal for women who desire pregnancy or who do not use any contraception and become pregnant, based on the Final Status CRF, will be summarized by treatment group. Time to event will be calculated as the date of pregnancy minus the date of removal plus one. Subjects who do not get pregnant will be censored at 12 months and failure time will be calculated as 12 months date minus the date of removal plus one. Subjects who initially desire to become pregnant after IUS discontinuation but do not complete a full 12 months before discontinuing the effort to achieve pregnancy will be excluded from the analysis.

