3.2.3 Other Secondary Outcome Measures

Other secondary outcomes that will be assessed for LNG20 and Mirena will include:

- Cumulative LNG20 pregnancy rates for years 2 through 10
 - Years 6, 7 and 8 will only include LNG20 subjects
 - Years 9 and 10 will only include the LNG20 16-35 year old enrollment group
- IUS continuation rates at 1 year, 2 years, 3 years, 4 years, 5 years, 6 years, 7 years, 8 years, 9 years and 10 years
 - Years 6, 7 and 8 will only include LNG20 subjects
 - Years 9 and 10 will only include the LNG20 16-35 year old enrollment group
- IUS expulsion rates at 1 year, 2 years, 3 years, 4 years, 5 years, 6 years, 7 years, 8 years, 9 years and 10 years
 - Years 6, 7 and 8 will only include LNG20 subjects
 - Years 9 and 10 will only include the LNG20 16-35 year old enrollment group
- IUS safety-related removal rates at 1 year, 2 years, 3 years, 4 years, 5 years, 6 years, 7 years, 8 years, 9 years and 10 years
 - Years 6, 7 and 8 will only include LNG20 subjects
 - Years 9 and 10 will only include the LNG20 16-35 year old enrollment group
- Vaginal bleeding patterns during IUS use
- Hemoglobin
- Adverse events, including clinically significant laboratory abnormalities
- Pregnancy outcomes will be obtained for all pregnancies that occur while a subject is using the IUS or if the date of conception is up to and including 7 days after IUS discontinuation, including normal births, septic abortions, ectopic pregnancies, birth defects, and premature deliveries, whenever this information can be obtained.
- Fertility rates during the first year following removal of the IUS for those women who desire pregnancy.

- Return to menses. Those women who are using non-hormonal contraceptive methods or no contraception (including those desiring pregnancy) will be followed for up to 3 months for the occurrence of menses following IUS discontinuation. Women who do not menstruate within 3 months following IUS discontinuation will be referred for appropriate evaluation and continue to be followed until menses has occurred or a diagnosis for the cause of the secondary amenorrhea has been established.
- Plasma levonorgestrel levels over the duration of IUS use
- Analysis an appropriate sampling of IUSs that are removed or expelled during the study

Other secondary outcomes that will be assessed for LNG20 will include:

- Plasma levonorgestrel levels over the first 14 days following LNG20 removal after 121 months of use

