- Removal of IUS, if not already expelled or removed (at an outside location)
- Retain all removed or expelled IUSs (when possible) per the Study Reference Manual
- Contraceptive counseling
 - Immediate initiation of another method in the office when possible
 - Request to use this method or be abstinent for at least one week to avoid conception within 7 days after IUS discontinuation
- Schedule next appointment

6.7 30-Day Safety Follow-Up

All subjects must have a safety follow-up visit between 30 and 43 days after the Treatment

Completion/Early Discontinuation Visit (except those made lost to follow up or who withdrew consent per section 7.18). If the subject contacts the office with an expulsion that was 30 or more days ago, this visit may be combined with the Early Discontinuation visit.

- Review of adverse events (note: all adverse events occurring within 30 days of IUS discontinuation should be reported on the appropriate adverse event CRF)
- Review of concomitant medications used up to 30 days of IUS discontinuation
- Menstrual history if not using a hormonal method of contraception
- High sensitivity urine pregnancy test (if positive, see Sections 7.4 and 7.5)
- Weight and blood pressure
- Additional contraceptive counseling if needed
- Review with subject that continued telephone or clinic follow-up (as appropriate) is indicated for the following:
 - an ongoing IUS-related adverse event at study discontinuation should be followed monthly until the adverse event resolves or has stabilized
 - any subject electing to use a non-hormonal contraceptive method or no contraception (including those desiring pregnancy) will be followed monthly for up to 3 months after IUS removal/expulsion for return of menses. Any woman who does not menstruate within 3 months following IUS discontinuation will be referred for appropriate evaluation and continue to be followed monthly until menses has occurred or a diagnosis for the cause of the secondary amenorrhea has been established
- Those women desiring a pregnancy after IUS discontinuation will be contacted every three months from their Treatment Completion/Early Discontinuation Visit up to one year to record return to fertility.
 - Once a pregnancy is reported no further follow-up contact is required.
 - Women who do not become pregnant and change their intention before completing a full 12 months of follow-up will be discontinued from the study and not be included in the return to fertility cohort.

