Dysmenorrhea (none, mild, moderate, or severe) will be summarized by the number and percentage of days with a particular pattern during each 84 and 90 day interval after enrollment through Month 24. After Month 24 dysmenorrhea will be summarized from the Adverse Events CRF. In addition, dysmenorrhea changes from baseline will be summarized using shift tables. Baseline dysmenorrhea is recorded on the Menstrual History CRF based on menstrual characteristics when not using hormonal contraception.

- **Adverse Events**

The number and percentage of subjects with each adverse event and serious adverse event will be presented by MedDRA system organ class, preferred term, and treatment group. Summaries will also be presented by relationship to the type of IUS or IUS insertion or removal procedure and the severity of the adverse event. All adverse events will be summarized with special attention to those events that may be related to an IUS, including:

- Difficult insertion or removal procedure;
- Perforation of the uterus;
- Dysmenorrhea;
- Low abdominal pain (not classified as dysmenorrhea);
- Uterine infection (including PID); and
- Other urogenital infections

- **Pregnancy Outcomes**

Pregnancy outcomes will be summarized by treatment group using the MITT population as well as listed by subject.

- **Fertility Rates**

Those women desiring pregnancy after leaving the study will be contacted every three months up to one year after IUS discontinuation to record any pregnancy. Kaplan-Meier methods will be used to estimate the probability of pregnancy over time.

- **Menses After IUS Discontinuation**

Those women who elect to use a non-hormonal contraceptive method or no contraception (including those desiring pregnancy) will be followed monthly for up to 3 months after IUS removal/expulsion for the occurrence of menses following IUS discontinuation.

Women who do not menstruate within 3 months following IUS discontinuation will be referred for appropriate evaluation and continue to be followed monthly until menses has occurred or a diagnosis for the cause of the secondary amenorrhea has been established.

Kaplan-Meier methods will be used to estimate the probability of the return of menses over time.

- **Plasma Levonorgestrel Levels**

- Levels over the lifespan of IUS use

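### The return-to-fertility analysis drops women who stop trying, admits some women only because they conceived, and credits unobserved pregnancy-free time up to 12 months

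*SAP*

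**What the plan says.** SAP 11.10 reports cumulative fertility rates for each month of the year after removal and sets three rules:

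- **Entry.** The cohort is "women who desire pregnancy or who do not use any contraception and become pregnant".
- **Censoring.** "Subjects who do not get pregnant will be censored at 12 months", and their time is computed to the 12-month date. No exception is stated for women whose contact ended sooner.
- **Exclusion.** Women who initially want pregnancy but "do not complete a full 12 months before discontinuing the effort to achieve pregnancy will be excluded from the analysis".

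Protocol 6.7 carries the same exclusion: women who do not conceive and "change their intention before completing a full 12 months of follow-up will be discontinued from the study and not be included" in the fertility cohort. It also sets the follow-up: women desiring pregnancy "will be contacted every three months from their Treatment Completion/Early Discontinuation Visit up to one year to record return to fertility".

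The protocol's outcome is narrower than the SAP's cohort. Protocol 3.2.3 lists "Fertility rates during the first year following removal of the IUS for those women who desire pregnancy". Under the fertility heading in Protocol 9.8, "Kaplan-Meier methods will be used to estimate the probability of pregnancy over time". SAP 1 gives the SAP precedence where the two differ on analysis.

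**The concern.** Return to fertility is a stated secondary objective (Protocol 2.2, SAP 2.2). Each rule distorts the rate in a known direction.

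1. **Stopping.** A woman who conceives in month 7 is kept. A woman who gives up in month 7 is removed, with seven months in which she tried and did not conceive. Membership depends on what happens after entry, which can only push the rate up.
2. **Event-only entry.** A woman using no contraception who does not state a wish for pregnancy counts only if she conceives. That too can only push the rate up. Reading the last three words of the phrase as applying to both groups does not help, because no non-pregnant woman would then be left to censor.
3. **Censoring at 12 months.** A woman last contacted at month 3 is treated as observed pregnancy-free to month 12, which pushes the rate down. Elsewhere the SAP does otherwise. In SAP 11.9, "Subjects without a continuation/expulsion/removal will be censored at the last contact date", and SAP 10.2.2 ends follow-up at the latest pregnancy assessment.

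A reader would take the published figure as the chance of conceiving within a year of removal. It would not be that, and the size and sign of the error would be unknown.

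**Working it through.** The plan states no fertility rate, cohort size, stopping rate or loss rate, so there is no figure to reproduce. All rates below are assumptions.

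**Ten-woman example.** Six conceive (months 2, 4, 5, 7, 9, 11), two are seen non-pregnant to month 12, and two leave at month 3.

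- Leavers censored at month 3: 1 - (9/10)(6/7)(5/6)(4/5)(3/4)(2/3) = 1 - 0.257 = 74.3%.
- Leavers classed as lost, hence censored at month 12: 6/10 = 60.0%.
- Leavers classed as having stopped trying, hence excluded: 6/8 = 75.0%.

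With nobody censored before month 12, Kaplan-Meier at 12 months is simply pregnancies divided by women retained. How the two leavers are labelled moves the answer by 15 points.

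**Monthly model.** Start with S = 1. Each month: conceive c = S·h; then stop a = (S - c)·s; then lost b = (S - c - a)·l; the remainder carries forward. Over 12 months, p is the total conceiving, L the total lost, and S12 those left. Assumed: h = 0.08 or 0.12, s = 0.5% to 5%, l = 0 to 2%. The target is 1 - (1 - h)^12, which is 63.2% at h = 0.08 and 78.4% at h = 0.12. Differences are in percentage points, from unrounded values.

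*Rule 1 alone (l = 0): p / (p + S12)*

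| h | s | p | S12 | Rate | Difference |
|---|---|---|---|---|---|
| 0.08 | 0.5% | 0.618 | 0.346 | 64.1% | +0.9 |
| 0.08 | 2% | 0.578 | 0.289 | 66.7% | +3.5 |
| 0.08 | 5% | 0.509 | 0.199 | 71.9% | +8.7 |
| 0.12 | 0.5% | 0.769 | 0.203 | 79.1% | +0.7 |
| 0.12 | 2% | 0.724 | 0.169 | 81.1% | +2.6 |
| 0.12 | 5% | 0.646 | 0.117 | 84.7% | +6.3 |

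*Rule 3 alone (s = 0): p / (p + L + S12), which equals p*

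| h | l | Lost | Rate | Difference |
|---|---|---|---|---|
| 0.08 | 1% | 7.0% | 60.5% | -2.8 |
| 0.08 | 2% | 13.3% | 57.8% | -5.4 |
| 0.12 | 1% | 5.5% | 75.4% | -3.1 |
| 0.12 | 2% | 10.6% | 72.4% | -6.0 |

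*Rules 1 and 3 together (l = 1% to 2%): p / (p + L + S12), stoppers removed*

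- Lowest, h = 0.12, s = 0.5%, l = 2%: 0.711 / (0.711 + 0.104 + 0.159) = 73.0%, about -5.4.
- Highest, h = 0.08, s = 5%, l = 1%: 0.489 / (0.489 + 0.053 + 0.176) = 68.1%, +4.8.
- h = 0.12, s = 3%: 78.8% with l = 1% (+0.4), but 75.6% with l = 2% (-2.9). A one-point change in monthly loss reverses the sign.

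*Rule 2 alone, k added conceivers per 100 women trying: (100·target + k) / (100 + k)*

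- h = 0.12: k = 2 gives 80.43/102 = 78.9% (+0.4); k = 10 gives 88.43/110 = 80.4% (+2.0).
- h = 0.08: k = 2 gives 65.23/102 = 64.0% (+0.7); k = 10 gives 73.23/110 = 66.6% (+3.3).

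*All three rules.* Adding k = 2 to the lowest case above gives (0.711 + 0.02)/(0.974 + 0.02) = 73.5%, or -4.9. Adding k = 10 to the highest gives (0.489 + 0.10)/(0.718 + 0.10) = 72.0%, or +8.7.

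**Check of the remedy.** Kaplan-Meier with stoppers and lost women censored in their own month returns 63.2% and 78.4% exactly, given non-informative stopping and loss.

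**The case against.** The best defence is that the stopping rule is deliberate. Protocol 6.7 and SAP 11.10 agree on it, and it could be read as describing women who kept trying until conception or month 12. That reading does not rescue the estimate: women who conceived early never had to show that they would have gone on trying, so the exclusion falls only on those who did not conceive.

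Several narrower points stand.

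- SAP 11.10 never says in words that lost women are carried to month 12. That is the literal effect of an unqualified rule. SAP 5.3 says missing data are not imputed unless otherwise specified, but it does not displace an explicit censoring date.
- The entry phrase may be loose drafting. Only women desiring pregnancy receive the three-monthly fertility contacts, so an incidental pregnancy may be all that is recorded for others.
- The SAP does not censor uniformly at last contact. SAP 11.11 censors return to menses at diagnosis of secondary amenorrhea.
- Kaplan-Meier is named in the protocol, not in SAP 11.10.
- The largest shift needs 5% monthly stopping, about 29% of women at h = 0.08, and no loss. At s = 2%, l = 1%, rules 1 and 3 nearly cancel: +0.3 points at h = 0.08 and -0.7 at h = 0.12.

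Such cancellation would be luck. It depends on rates the documents do not give.

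**Conclusion.** The concern holds. Followed as written, SAP 11.10 does not estimate the probability of conceiving within a year of removal among women who want to. Excluding stoppers and event-only entry inflate the rate; censoring all remaining non-pregnant women at 12 months deflates it. Over the assumed range the net error from the exclusion and the censoring runs from about -5.4 to +4.8 points. Event-only entry adds 0.4 to 3.3 points when applied alone. These sizes rest on constant, independent monthly rates chosen for illustration; the direction of each rule does not depend on them.

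This should be fixed but is not critical. The outcome is secondary and descriptive, no formal test uses it, and the Pearl Index is unaffected.

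**What to change.** In SAP 11.10:

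1. Define the cohort as women who state at discontinuation that they desire pregnancy, in line with Protocol 3.2.3.
2. Keep women who later stop trying.
3. Censor non-pregnant women at the earliest of stopping the attempt, restarting contraception, last contact, or 12 months, dating a stop to the nearest three-monthly contact.
4. Delete the clause admitting non-contracepting women who conceive, and list those pregnancies separately.
5. Name Kaplan-Meier as the estimator.

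In Protocol 6.7, say that women who change intention may leave follow-up but stay in the cohort as censored. The rate with stoppers excluded may remain as a labelled sensitivity analysis.

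**Cost.** SAP wording and one protocol sentence, which needs an amendment and, if required, IRB approval (Protocol 10.3.13). No new visits are needed. No passage says that the date of stopping is recorded, so it is known only to about three months. In the same model at s = 5%, dating departures to the next or previous contact moves the corrected rate by about -2.0 to +1.8 points with no loss, and -2.7 to +2.5 with 2% monthly loss. That error can exceed the bias where rules 1 and 3 happen to cancel. Censoring at stopping may also be informative if women stop because they are not conceiving, so the bias is reduced but not necessarily removed. The reported rate may be less favourable.
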